2.0 STUDY SYNOPSIS

Title of Study:	Immunologic Efficacy of Heplisav B Vaccine in Patients Undergoing Treatment with Immunosuppressive Medications
Sponsor:	Baylor Scott and White Research Institute
Phase of Development:	Phase 1 (Medically immunosuppressed subjects)
Objectives:	Preliminary trial of Heplisav-B vaccine in medically immunosuppressed patients with co-primary objectives of vaccine immunogenicity and patient safety
Study Design:	This is an open label exploratory study of the immunologic efficacy and safety of an FDA licensed HBV vaccine that contains HsAg-1018 adjuvant which has TLR 9 agonist properties (Heplisav-B). It will be used in patients treated with long term immunosuppressive drug therapy. The patients will be given two doses of Heplisav-B, the first delivered at the baseline visit and the second at week 4. Anti-HBs titers will be determined at baseline and at weeks 4, 8, 12, 24 and 60. The proportion of those with seroprotective anti-HBs levels and the geometric mean titers of anti-HBs at each time interval will be compared with those observed in phase III trials of immunocompetent individuals receiving the same dosing schedule. Individuals who fail to demonstrate protective levels of anti-HBs at week 8 will be given a third booster dose at week 12.
Study Population:	A total of 18 patients will be entered into the study including 3 evenly sized groups of 6 as follows: Group A patients are taking tumor necrosis factor alpha or interleukin inhibitor therapy for underlying chronic inflammatory disorders; Group B patients are taking chemotherapy for solid organ malignancy; and Group C patients are either recipients of livers from anti-HBc positive donors or individuals transplanted for chronic HBV infection without recurrent hepatitis B at the time of enrollment. Serologic Characteristics Per Group: All patients in Groups A and B must be HBsAg negative but anti-HBc positive to qualify indicating that they have serologic evidence for resolved hepatitis B. Those with low titer (<20 mIU) antibody will not be specifically excluded permitting observation of a possible anamnestic anti-HBs response. Patients in Group C will have either a remote history of liver transplant for HBV or receipt of an anti-HBc positive donor liver. Eligibility requires HBsAg to be negative w/wo anti-HBc reactivity.

Safety Evaluation:	Yes
Efficacy Evaluation:	Yes

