Schedule of Events:	In the absence of appropriate documentation, all patients will initially be screened for HBsAg, anti-HBc, and anti-HBs status by qualitative testing at a screening visit. Patients in Group A and B found to be anti-HBs positive will be tested for anti-HBs quant within one week to confirm final eligibility. Two doses of Heplisav-B will be administered at a baseline visit and 4 weeks later. Anti-HBs levels will be assessed at the baseline visit and again at weeks 4, 8, 12, 24 and 60. All patients who fail to respond with seroprotective anti-HBs levels (≥ 10 mIU/mL) at week 8 will be given a third dose of vaccine at week 12 and followed until week 60. Liver transplant patients (Group C) will be vaccinated and followed in the same manner as Groups A and B.

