6.1. Primary Study Endpoints/Secondary Endpoints

Primary endpoints: determination of (1) adequate safety and (2) immunologic efficacy of Heplisav-B in patients taking ISDT. Immunologic efficacy will be determined by the seroprotection rate (SPR) or percentage of patients who have anti-HBs titers greater than 10 mIU/ml at weeks 24 and 60. Secondary endpoints include (1) determination of the percentage of patients with anti-HBs titers ≥ 100 mIU/ml at weeks 24 and 60. Both (1) and (2) as well as geometric mean titer of anti-HBs at all study visit intervals will be will be compared to those observed with historical immune competent cohorts who received identical dosing with Heplisav-B. An additional secondary endpoint will to determine the proportion of patients on ISDT who require a third dose of vaccine to induce seroprotective level of anti-HBs.

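### Section 6.1 says the historical cohorts had identical dosing, but they had two doses, and at weeks 24 and 60 this trial's results include week-8 non-responders given a third

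*Protocol*

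**What the plan says.** Section 6.1 defines the primary immunologic endpoint as the "percentage of patients who have anti-HBs titers greater than 10 mIU/ml at weeks 24 and 60". It then says that "Both (1) and (2) as well as geometric mean titer of anti-HBs at all study visit intervals" will be "compared to those observed with historical immune competent cohorts who received identical dosing with Heplisav-B". The numbering is loose: the secondary list has only an item (1), while in the primary list (1) is safety and (2) is immunologic efficacy, that is, SPR. The synopsis (2.0, Study Design) is clearer. It compares both the seroprotected proportion and the geometric mean titre (GMT), at every time interval, with "those observed in phase III trials of immunocompetent individuals receiving the same dosing schedule".

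The same synopsis entry says: "Individuals who fail to demonstrate protective levels of anti-HBs at week 8 will be given a third booster dose at week 12". Its Schedule of Events row says that these patients "will be given a third dose of vaccine at week 12 and followed until week 60". Sections 4.4 and 4.7 agree that the dose is given; the footnote to Table 1 says it is offered.

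Section 4.0 describes two trials in immunocompetent adults and, separately, one in chronic kidney failure. Heplisav-B was given as two doses four weeks apart in the former and as three injections in the latter.

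Section 6.1 also lists, as a separate secondary endpoint, the "proportion of patients on ISDT who require a third dose of vaccine to induce seroprotective level of anti-HBs". Sections 6.0 and 11.1 call the study exploratory and descriptive.

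**The concern.** The trial has no concurrent control, so the historical cohorts are its only external benchmark. A reader told that dosing was identical will put any difference in SPR down to immunosuppression or other differences in population. At weeks 24 and 60 that reading is not safe. Patients who failed two doses have by then had another dose that the comparison cohorts did not have, and no passage says how they count in the comparison.

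Because the third dose goes only to failures, its own effect on SPR is upward. The week-24 and week-60 rates can therefore look closer to the immunocompetent rate than two doses made them. Section 11.2 says the trial is meant to show whether further studies are warranted, so an accurate description of the benchmark matters even without a formal test.

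**Working it through.** The protocol states no figure for this comparison, so there is none to reproduce. The check sets the dosing on each side next to each other and then works out what one patient weighs.

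**Dosing by visit (sections 2.0, 4.0, 4.4, 4.7 and Table 1)**

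| Visit | This trial | Immunocompetent cohorts (4.0) | Same dosing? |
|---|---|---|---|
| Week 8 | two doses | two doses | yes |
| Week 12 | two doses, if blood is drawn before any third dose | two doses | yes, on that condition |
| Weeks 24 and 60 | two doses, or three for week-8 non-responders | two doses | no |

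The kidney-failure trial does not close the gap. Its patients were randomized to three injections, not given a third for non-response, and section 4.0 lists it apart from the immunocompetent trials. The rationale text later groups kidney failure with immunocompetent recipients, but a fixed three-injection regimen is still not this trial's regimen.

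A smaller departure runs through all these visits. Section 4.7 omits the second dose when the titre is at least 300 mIU/ml after the first (an event it calls unlikely), and section 6.7 allows dosing to be withheld. Patients with fewer than two doses can shift the comparison the other way, so no net direction is claimed.

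**Weight per patient (section 11.2: 18 patients, three groups of 6)**

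Let c be the number of third-dose recipients who are seroprotected at the visit. The gap between SPR as observed and SPR with third-dose recipients counted as non-responders is 100 × c/18 points overall. If all c are in one group, it is 100 × c/6 points in that group.

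| c | Overall (points) | Within one group (points) |
|---|---|---|
| 1 | 5.6 | 16.7 |
| 2 | 11.1 | 33.3 |
| 3 | 16.7 | 50.0 |

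This gap is the most the third dose can have added, provided it never lowers a titre below the threshold. The true contribution is smaller if some of the c would have converted without it.

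**Illustration on assumed rates**

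Let p be the share seroprotected at week 8 and maintained, and r the share of week-8 non-responders converted by the third dose. Then SPR = p + (1 − p) × r, and the gain is (1 − p) × r. The protocol gives neither p nor r.

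- p = 0.9, r = 0.2: gain 0.1 × 0.2 = 2 points.
- p = 0.5, r = 0.4: gain 0.5 × 0.4 = 20 points.
- p = 0.3, r = 0.6: gain 0.7 × 0.6 = 42 points.

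Treating patients as independent, the chance that at least one of 18 qualifies for a third dose is 1 − p^18: 85% at p = 0.9 and 99.8% at p = 0.7. So the mismatch will probably arise, but its size depends wholly on the assumptions.

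**The case against.** The best defence is that the claim of identical dosing means the planned two-dose series. Section 4.4 supports this: it states the two doses, then the historical comparison, and only then the booster as a contingency. The synopsis wording can fairly be read the same way. This softens the charge to one of unclear wording, but it does not repair the comparison. On either reading, patients converted by a third dose count as successes at weeks 24 and 60 against cohorts that had two.

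It can also be said that the booster's role is already visible, since the proportion needing a third dose is a secondary endpoint and the synopsis plans comparisons at weeks 8 and 12. That is true and limits the harm. It does not correct the description of the comparison at the primary time points, or show SPR there without booster conversions. Table layout can be left to the SAP, but the SAP should not have to contradict a protocol statement about the comparator.

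Three further points stand:

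- That SPR is part of the 6.1 comparison is an inference from loose numbering, though the synopsis states it outright.
- Matching the number of doses does not match the populations. Groups A and B are anti-HBc positive, and baseline anti-HBs below 20 mIU/ml is allowed, whereas section 4.3 describes the phase III patients as non-infected and immune competent.
- With no test, margin or threshold tied to the historical rate, no formal decision can go wrong.

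**Conclusion.** The concern holds and should be fixed. The property section 6.1 claims for its comparator does not hold at weeks 24 and 60, the only time points at which it sets the primary SPR. The synopsis is open to a two-dose reading but applies the comparison at every interval, so it needs clarifying too.

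The firm statement of size is the weight of one patient: 5.6 points overall, 16.7 within a group. The 2 to 42 points in the illustration is not an estimate for this trial. The conclusion rests on section 4.0's description of the immunocompetent cohorts as two-dose. The consequence is a descriptive comparison that can flatter the two-dose regimen.

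**What to change.** 1. **Wording.** In 6.1, replace the claim of identical dosing with a statement that the historical cohorts had the two-dose series and that results after week 12 include third-dose recipients. Clarify the synopsis in the same way. State which items the reference to (1) and (2) in 6.1 covers. Reconcile the passages that say the third dose is given with the Table 1 footnote that says it is offered.
2. **Two-dose comparison.** Treat the planned week-8 and week-12 historical comparisons as the ones matched on dosing, and say that the match is on dosing only. Specify that the week-12 sample, already in Table 1, is drawn before any third dose. Identify any patient who had fewer than two doses. The primary time points stay at weeks 24 and 60.
3. **Weeks 24 and 60.** Show SPR against the historical rate twice: as observed for the whole regimen, and with third-dose recipients counted as non-responders. Do the same for the 100 mIU/ml rate if 6.1 is meant to include it. Show GMT by number of doses received. Do not set the two-dose subset's GMT against a whole-cohort historical GMT, because that subset leaves out the week-8 failures who took a third dose.

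The cost is a few sentences and one extra tabulation from data already collected. No visit, sample, patient or dosing rule changes. The drawbacks are that the week-24 and week-60 result becomes a less favourable range, and its lower figure is deliberately conservative because it also fails anyone who would have responded late without the third dose. The GMT subsets will be very small.

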6.2. Study Design/Type

This is an open label study of 18 patients taking long term immunosuppressive drug therapy.

- **6.3. Randomization**—Not applicable
- **6.4. Maintenance** Not applicable
- 6.5. Trial Treatment

See Study Synopsis (2.0) and Figure 1

6.6. Duration

The protocol includes a 52 week observation period after two doses of vaccine.

6.7. Premature Drug Discontinuation

Further dosing of Heplisav-B will be withheld in the following situations:

- 1. For all groups: A grade 3 AE or SAE that is considered to be possibly or definitely related to Heplisav-B.
- For Group A patients: A significant clinical worsening of their inflammatory disorder or development of a new onset pIMMC after one or two doses of vaccine regardless of relatedness.

- 3. If the patient requests not to continue with dosing or if is the opinion of the investigator that further dosing should be withheld.
- 4. If the patient develops transplant rejection that is possibly or definitely vaccine related.

Indications for participant withdrawal in are further outlined in sections 7.3.

6.8. Product Accountability

All vaccine will be kept in a locked refrigerator to which only the principal investigator and clinical coordinator have access. This refrigerator is immediately proximate to the clinic where patients will be seen. A log of doses dispensed and those remaining will be kept for each patient by the study coordinator and will be made available to the principal investigator and sponsor upon request.

6.9. Data Identification

CRFs will include: (a) patient age, sex, (b) Group (c) baseline serologic status, (d) results of anti-HBs quantification, CRP, and AST and ALT levels, (e) immunosuppressant medications, and (f) any potential short or long term adverse events with plan of management. Items (d), (e), and (f) will be recorded for each interval.

7.0. SELECTION AND WITHDRAWAL OF SUBJECTS

7.1. Inclusion Criteria

- 1.) Age 18 or older and agree to adhere to the requirements of the study
- 2.) Must be willing to provide informed consent
- 3.) Serologic profile consistent with resolved hepatitis B (HBsAg negative but anti-HBc positive*)
- 4.) Recipient of anti-HBc positive liver (Group C).
- 5.) Chronic inflammatory disease requiring TNF or interleukin inhibitor therapy (Group A)
- 6.) Solid organ malignancy that requires systemic cancer chemotherapy
- 7.) Post liver transplant for chronic HBV infection (Group C).
- 8.) Recipient of immunosuppressive drug medication as described above

7.2. Exclusion Criteria

- 1.) HBsAg positivity
- 2.) Anti-HBs titer ≥ 20 mIU/mL at baseline
- 3.) HIV infection**
- 4.) HCV infection**
- 5.) Prior hepatitis B vaccination
- 6.) Receipt of hepatitis B immune globulin during the past 4 months
- 7.) Hematologic malignancy

- 8.) Hepatocellular carcinoma
- 9.) Active alcohol use > 20 grams daily
- 10.) Unstable underlying inflammatory disorder
- 11.) Pregnancy or breast feeding
- 12.) History of severe depression or other severe psychiatric disorder
- 13.) Receipt of liver allograft < 3 years earlier
- 14.) Transplant rejection within the past year
- 15) Individuals having unstable or poorly responsive inflammatory disorders
- 16) All persons who are judged by the investigator to have an unreasonable risk of complications
- 17) Anticipated life expectancy less than one year

Footnotes to Inclusion/Exclusion Criteria *There must be evidence of anti-HBc positivity at the screening visit and if so, documentation that this is chronic in nature will be obtained from a review of the electronic record (for example, history of past exposure, past serology documentations). If documentation is lacking, however, then an IgM anti-HBc test will be at done at the screening visit to confirm that the patient has not recently acquired hepatitis B.

**Serologic testing for HCV and HIV must be within 4 months of potential eligibility. If this is not the case, the testing will be repeated at the screening visit.

7.3 Vaccine Withdrawal

Need for vaccine withdrawal and subject withdrawal (see Section 7.4 below) will be assessed by application of the grading criteria for adverse events as described in the Common Terminology Criteria for Adverse Events as published by the US Department of Health and Human Services/National Institutes of Health, and the National Cancer Institute (version 5.0, November 2017). A three point scale will be used to judge relatedness: unrelated, possibly related, and definitely related. *Possibly related* will be defined as any AE in which there is a reasonable time sequence to vaccination but the AE could be explained by another potential cause such as other drugs or events, patient noncompliance with immune suppression medication, or recent switch in immune suppression medication. Definitely related will require a plausible time relationship to vaccine administration that cannot be explainable by other events and condition as described above. Also, it will be further considered to be definitely related if there is a response to withholding further vaccination.

1. Any patient in Group A who is deemed to have significant clinical worsening of their inflammatory disorder or develop a new onset pIMMC after one or two doses of vaccine will be withdrawn from further dosing regardless of relatedness to the vaccine. However, the subject will be followed until week 60 to collect additional safety data. During this time, additional immunogenicity data may be obtained if the patient had received at least two doses of vaccine

before clinical worsening became apparent and if seroprotective levels were observed when last tested.

2. Regardless of which group a patient belongs to, any subject who has a Grade 3 AE or SAE will not receive further vaccination if the adverse event is considered to be possibly or definitely related to Heplisav-B. Each of these patients will continue to be seen at the visits specified in the protocol until the end of the study (week 60) so that additional safety data may be collected.

Additional immunogenicity data may be obtained if the patient had received two doses of vaccine before the AE became apparent and if seroprotective levels of anti-HBs were evident when last tested.

3. Transplant rejection suspected by unexplainable increase in liver enzymes *and* proven by liver biopsy will be considered as a Grade 3 AE that requires medical intervention (MAAE). Each patient with rejection will be withdrawn from further vaccination if the rejection is considered to be possibly or definitely related to the vaccine. Such patients will be followed until the end of the study (week 60) so that additional safety data may be collected. Additional immunogenicity data may be obtained if the patient had received at least two doses of vaccine before allograft rejection became apparent and if seroprotective levels were evident when last tested.

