4.7. Schedule of Events

The schedule of events can be seen in Table 1. Patients will be seen and consented at a screening visit to determine eligibility. It is anticipated that most if not all of the serologic data needed to qualify the patient will be available by review of electronic records at the screening visit. If not, one or more of the serologic HBV markers will be tested at screening. The serologic studies for HBV must have been done within the past year. Turnaround times are less than 5 days and so there should be no lagging data needed at the time the patients receive their first dose of vaccine 28-30 days later. There will also be a 28-30 day window between the first vaccine inoculation visit and the second vaccine inoculation visit. The 12, 24, and week 60 visits will have a one week \pm window.

In the event of an intercurrent acute illness that either places the patient at added risk or makes vaccine adverse event relatedness difficult to interpret, every effort will be made to bring the patient back when the illness is resolved and preferably no longer than one week of the initially specified time.

Heplisav-B vaccine will be delivered at the baseline/enrollment visit (visit # 2 considered to be day 0) and again 4 weeks later. In the unlikely event that anti-HBs titer is ≥ 300 mIU/mI after a single dose of vaccine, patients will not be given a second dose. All individuals who do not have protective levels of anti-HBs (> 10 mIU/mI) after two doses at week 8 will be given a third identical dose of vaccine at the week 12 visit.

Adverse events (e.g, localized skin reactions, fever) that occur soon after vaccination will be assessed by weekly telephone assessments and patients will be asked to record changes in underlying disease activity on a Patient Related Outcome Measurement form. These will be distributed at the enrollment visit and subsequent visits. They will initially be completed by the patient and completed as needed by the investigator and coordinators at all study visits. Data on all AEs will be recorded on an Adverse Event Data Capture form (Appendix 1). These will be filled out by the study coordinator in conjunction with the investigator at each visit.

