9.0 ASSESSMENT OF EFFICACY

9.1 Efficacy Parameters

- Assessment of proportion of subjects with anti-HBs titers ≥ 10 mIU/ml at each study interval.
- Assessment of percentage of subjects with anti-HBs titers ≥ 100 mIU/ml at each study interval.

- Assessment of geometric mean titers for all subjects at each study interval.
- Assessment of reasonable safety in patients who are medically immunosuppressed

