9.2 Method and Timing

Assessment of efficacy will require quantitative anti-HBs assessments at each of the visits that are specified in Table 1. This includes week 4,8,12, 24 and 60 week visits.

10. 0. ASSESSMENT OF SAFETY

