^{** 5%} of recipients of anti-HBc donor liver are anticipated to be anti-HBc positive. These patients will be excluded if anti-HBs also > 20 mIU/ml. Patients transplanted for HBV infection are anticipated to be anti-HBc positive

[#] If anti-HBs level remains < 10 mIU/ml

TABLE 1. Study Participation Table

	Visit 1: Screening	Visit 2 Enrollment/ Baseline	Visit 3 4 Week Follow up (+/- 3-5 d)	Visit 4 8 Week Follow up (+/- 3-5 d)	Visit 5: 12 Week Follow Up (+/- 3-5 d)	Visit 6: 24 Week Follow Up (+/- 1 week)	Visit 7: 60 Week Follow Up (+/- 1 week)
Read and Sign Informed Consent	Х						
Medical History	Х						Х
Review of Immunosuppresants	Х	Х	Х	Х	Х	Х	Х
Interview, brief physical	Х	Х	Х	Х	Х	Х	Х
Vital Signs (heart rate, blood pressure, temperature)	Х	Х	Х	Х	Х	Х	Х
Missing HBV blood testing*	Х						
Quant anti-HBs	X [≠]	Х	Х	Х	Х	Х	Х
CRP**		Х	Х	Х	Х	Х	Х
Pregnancy test [¥]	Х	Х	Х		Х	X _∞	
Hepatic function panel		Х	Х	Х	Х	Х	Х
Patient Related Outcome Form for Inflammatory Disorder		Х	Х	Х	Х	Х	Х
Repository Blood Sample (for repeat antibody test)		Х	Х	Х	Х	Х	Х
Vaccine Administration, with observation for reactions		Х	Х		X***		
Adverse effects form [±]			Х	Х	Х	Х	Х

^{*} Test for anti-HBs, anti-HBc, or HBsAg if not in the medical record or > one year previously. Test for HIV and HCV antibody is not within 4 months of screening.

[≠] Only done at this visit if medical record indicates patient is anti-HBs positive by qualitative testing.

^{**} This will only be done in patients taking TNF or interleukin inhibitor therapy for chronic inflammatory disorders.

[¥] If potentially child bearing female. Patients who are positive will not be eligible.

^{***} A 3rd dose will be offered to those participants who lack seroprotection (>10 mIU/ml) at week 8.

[±] Observation for adverse events includes weekly telephone calls for 4 weeks after each vaccine dose.

 $[\]infty$ If patient requires third dose of vaccine as per protocol.

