Abdominal Pain	None	On a scale 1-10 (with 10 being the worst) 1 2 3 4 5 6 7 8 9 10	On a scale 1-10 (with 10 being the worst) 1 2 3 4 5 6 7 8 9 10	On a scale 1-10 (with 10 being the worst) 1 2 3 4 5 6 7 8 9 10	
Systemic					
Fever	YES/NO	99-101 F	> 101 to 103 F	> 103	
Fatigue	YES/NO	Minimal	Moderate	Severe	
Overall assessment*	No change	Feel slightly worse	Feel moderately worse	Feel much worse	
Social Function					
	Normal	Occasional limitation	Several times weekly	Absence from work	Home ridden
Food tolerability	No problem	Minimally affected	Moderately affected	Severely affected	

Comments	 	 	

Appendix 3. Quick View Table of Criteria for Subject Withdrawal, Vaccine Withdrawal, and Study Termination

Adverse Event	Relatedness	Subject	Vaccine	Anticipated Follow up	Study Termination
	Not Poss Def	withdrawal	Withdrawal		
Death	Not	-	-	-	No*
	Possibly	-	-	-	Yes
	Definitely	-	-	-	Yes
Grade 4	No	No	No	Until 52 weeks after last vaccine dose	No*
	Possibly	Yes	Yes	Until 52 weeks after last vaccine dose	Yes
	Definitely	Yes	Yes	Until 52 weeks after last vaccine dose	Yes
Worsened underlying	Regardless of	Yes	Yes	Until 52 weeks after last vaccine dose	No, but hold on further enrollment & vac-
disease in Group A patient	relatedness				cine in group A if AE is definitely related**
	Not	No	No	Until 52 weeks after last vaccine dose	No
	Possibly	No***	Yes	Until 52 weeks after last vaccine dose	No
Grade 3 AE or SAE in any	Definitely	No***	Yes	Until 52 weeks after last vaccine dose	Yes, if a second patient in different group
patient group					has a Grade 3 AE or SAE that is also
					definitely related to vaccine $^{\Omega}$ If this does
					not occur, a hold on further enrollment &
					vaccine in the group the patient belongs to
Liver allograft rejection	Possibly	No***	Yes	Until 52 weeks after last vaccine dose	No
	Definitely	No***	Yes	Until 52 weeks after last vaccine dose	Yes, if a second patient in different group
					has a Grade 3 AE or SAE that is also
					definitely related to vaccine $^{\Omega}$ If this does
					not occur, a hold on further enrollment &
					vaccine in group C will be enacted.

^{*}The finding of a death or Grade 4 AE that is considered unrelated to vaccine will not be considered sufficient to terminate the study nor place a hold on further enrollment in that group.

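### Section 7.3 lets a patient's last anti-HBs titre decide whether later titres are collected after vaccine withdrawal, in conflict with 9.1, 9.2 and Table 1

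*Protocol*

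**What the plan says.** Section 7.3 describes three situations in which vaccination stops but follow-up continues to week 60 for safety. Each carries a condition on further antibody testing.

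- Item 1 (Group A worsening or a new immune-mediated condition): at least two doses must have been received "before clinical worsening became apparent and if seroprotective levels were observed when last tested".
- Item 2 (related Grade 3 AE or SAE, any group): "Additional immunogenicity data may be obtained if the patient had received two doses of vaccine before the AE became apparent and if seroprotective levels" were evident at the last test.
- Item 3 (biopsy-proven rejection): "Additional immunogenicity data may be obtained if the patient had received at least two doses of vaccine before allograft rejection became apparent and if seroprotective" (the sentence closes by referring to the titre at the last test).

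The efficacy sections carry no such condition. Section 9.1 lists "Assessment of geometric mean titers for all subjects at each study interval", together with the proportions at or above 10 and 100 mIU/mL at each interval. Section 9.2 states: "Assessment of efficacy will require quantitative anti-HBs assessments at each of the visits that are specified in Table 1". Table 1 marks quantitative anti-HBs at every visit from baseline to week 60, and no footnote exempts patients withdrawn from vaccine. Section 6.1 makes the seroprotection rate at weeks 24 and 60 the primary immunologic endpoint.

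**The concern.** The two sets of instructions cannot both be followed. At week 24, a coordinator seeing a vaccine-withdrawn patient whose last titre was below 10 mIU/mL is told by Table 1 to draw the sample, and by 7.3 that the condition for obtaining it is not met.

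If 7.3 prevails, data are missing because of the outcome itself. Non-responders who stop vaccination drop out of the later titres while responders may stay in. The patients still attend, so the loss is avoidable, and a titre that was never measured cannot be restored by an analysis method. Section 6.1 then sets these results against historical immunocompetent cohorts, so an upward distortion would flatter the vaccine in that comparison.

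**Working it through.** **Inputs.** 18 patients in three groups of six (11.2; 3 × 6 = 18). There is no power calculation to reproduce, and the protocol gives no expected withdrawal rate, response rate or titre distribution. All sizes below therefore rest on stated assumptions.

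**Step 1: how the condition acts.**

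- *Titre limb.* It removes patients who were low at the last test, so the rate and GMT among tested patients are pushed mainly upward.
- *Dose limb.* It can act the other way. Under 4.7, at a titre of 300 mIU/mL or more "after a single dose of vaccine, patients will not be given a second dose". Such a patient, if later withdrawn from vaccine under 7.3, has had only one dose and fails the condition despite a very high titre.
- *Timing.* Table 1 measures anti-HBs at week 4, the visit of dose 2, and next at week 8. For an event between those visits, the last available titre can be the week-4 one, which reflects one dose only.
- *Follow-up for Group A.* Section 7.3 item 1 follows the subject to week 60. The Appendix 3 row for worsened underlying "disease in Group A patient" gives subject withdrawal as Yes and follow-up to 52 weeks after the last dose. After one dose that is 0 + 52 = week 52; after two doses, 4 + 52 = week 56. Both precede the week-60 visit, whose window opens at 60 − 1 = week 59.

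**Step 2: effect of one untested patient.** Assume responders have 100 mIU/mL and non-responders 5 mIU/mL, and analyse tested patients only. With r responders and n non-responders tested:

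rate = r/(r + n); GMT = 10^[(r·log10 100 + n·log10 5)/(r + n)]

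| Scenario | All tested | One untested |
|---|---|---|
| 18 patients, non-responder untested | 9/18 = 50.0%, GMT 22.4 | 9/17 = 52.9%, GMT 24.4 |
| 18 patients, non-responder untested | 15/18 = 83.3%, GMT 60.7 | 15/17 = 88.2%, GMT 70.3 |
| Group of 6, non-responder untested | 3/6 = 50%, GMT 22.4 | 3/5 = 60%, GMT 30.2 |
| Group of 6, non-responder untested | 5/6 = 83.3% | 5/5 = 100% |
| 18 patients, one-dose responder untested | 9/18 = 50.0%, GMT 22.4 | 8/17 = 47.1%, GMT 20.5 |
| Group of 6, one-dose responder untested | 3/6 = 50%, GMT 22.4 | 2/5 = 40%, GMT 16.6 |

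The last two rows suppose that the one-dose responder's titre has fallen to 100 by the visit in question. If it is still 300, the all-tested GMT is 23.8 (18 patients) or 26.9 (six), and the one-untested figures do not change.

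**Step 3: expected inflation of the rate.** If the true rate is p and a fraction w of non-responders goes untested:

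inflation = p/[p + (1 − p)(1 − w)] − p

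- p = 0.5: w = 0.1 gives 0.5/0.95 − 0.5 = +2.6 points; w = 0.2 gives 0.5/0.90 − 0.5 = +5.6 points.
- p = 0.8: w = 0.1 gives 0.8/0.98 − 0.8 = +1.6 points; w = 0.2 gives 0.8/0.96 − 0.8 = +3.3 points.

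**Step 4: allowing status to change after the last test.** Let q be the fraction withdrawn from vaccine (independent of response), r the fraction seroprotected at the last test, and s1 and s0 the later seroprotection in those with and without it. The true rate is r·s1 + (1 − r)·s0. The tested-only rate is [r·s1 + (1 − r)(1 − q)·s0]/[r + (1 − r)(1 − q)].

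- Largest case examined (q = 0.3, r = 0.4, s1 = 0.9, s0 = 0.1): true 0.420, observed 0.402/0.82 = 0.490, +7 points.
- Smallest case (q = 0.1, r = 0.8, s1 = 0.9, s0 = 0.3): true 0.780, observed 0.774/0.98 = 0.790, +1 point.

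**The case against.** - **Section 7.3 is permissive and specific.** It does not forbid testing, and a specific clause can be read as an exception to a general schedule. Section 7.5 also keeps patients stopped for safety on study visits. This stands in part: the risk is ambiguity rather than a ban. But the clause still ties collection to the last titre, 7.5 gives safety data as the purpose of those visits, and nothing says which instruction governs.
- **The two-dose limb has a reason.** Section 6.1 compares with cohorts dosed identically. That can justify an analysis subset; it does not justify leaving the titre unmeasured. Patients given a third dose also depart from the two-dose schedule and are still tested to week 60.
- **Appendix 3 has a footnote following vaccine-withdrawn patients to week 60.** Its wording is general, but its marker is attached to the Grade 3 and rejection rows, not to the Group A row. Elsewhere the 52 weeks is a minimum. The discrepancy in that row remains.
- **The inflated rate depends on the denominator.** This is correct. If untested patients count as failures, the rate is not inflated. The denominator may properly be left to a SAP and is not criticised here. That choice would still hide late seroconversion and would not supply a GMT.
- **Stored samples could rescue the titres.** Table 1 keeps a repository sample at each visit from baseline, for repeat antibody testing. Some titres may be recoverable, but the protocol does not assign the samples to this use.
- **The trial is small and descriptive.** The exact 95% interval for 9/18 runs from 26.0% to 74.0%, far wider than a shift of 2.9 points. The one-dose responder with a very high titre is also a case that 4.7 itself regards as unlikely. Both points limit the severity but do not remove the contradiction.

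**Conclusion.** The concern holds. Section 7.3 contradicts 9.1, 9.2 and Table 1 on whether anti-HBs is measured after vaccine withdrawal. Following 7.3 makes availability of the week-24 and week-60 outcome depend on an earlier titre. The bias is predominantly upward, with a possible but rarer downward route through the two-dose condition.

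Among tested patients, one missing non-responder moves the rate by about 3 to 5 points over 18 patients and by 10 to 17 points in a group of six, in the examples shown. Expected inflation over the assumed ranges is roughly 1 to 7 points. These sizes rest on assumed response and withdrawal rates and a tested-only denominator; the GMT figures also rest on the assumed titres. The contradiction rests on none of these. Only vaccine-withdrawn patients are affected, so this should be fixed but does not undermine the trial as a whole.

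**What to change.** In 7.3 items 1 to 3, replace the conditional sentence with: *Anti-HBs will be measured at all remaining scheduled visits in every patient still followed, regardless of the number of doses received and the last titre.*

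Reconcile 7.3 item 1 with the Group A row of Appendix 3 on whether the subject is withdrawn from the study and whether follow-up reaches the week-60 titre.

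The cost is three sentences, one table row and a few extra anti-HBs assays at visits or follow-up already planned. The collection change needs no alteration to any dosing or withdrawal rule.
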